9.4 Description of Statistical Methods

9.4.1 Analysis of the Primary Efficacy Endpoint

Our primary aim is to assess the feasibility of the intervention. There are no relevant statistical endpoints.

9.4.2 Analysis of the Secondary Endpoints

Our secondary endpoints are concentrations of bisphenols and phthalate metabolites in breastmilk and infant urine. We will perform t-tests to compare distributions of chemicals between the two infant groups to assess the effectiveness of the intervention. We will also assess correlations of concentrations of individual bisphenols and phthalate metabolites between mothers and children from the control group to assess the relative prevalence of these chemicals in diet (measured in maternal breast milk) vs. baby products (infant urine).

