Reference Therapy	Half of the participants will be randomly assigned to the control group and provided with a three-month supply of conventional disposable diapers (e.g., Huggies or Pampers) and baby products (e.g., wipes, diaper cream).
Key Procedures	Three-month adherence to diaper assignment and one-time infant urine collection and maternal breast milk collection.
Statistical Analysis	Our primary aim is to assess the feasibility of the intervention; the project is not adequately powered to detect statistically significant differences between groups. However, we will compare distributions of chemicals between the two infant groups to assess the effectiveness of the intervention and also between mothers and children from the control group to assess the relative prevalence of particular bisphenols or phthalates in diet (reflected in maternal breast milk concentrations) vs. baby products (reflected in infant urinary concentrations).

CONFIDENTIAL

Schematic of Study Design

Key Roles

[name], MPH (Principal Investigator)

Assistant Professor, Department of Pediatrics, NYU Grossman School of Medicine
[name]
[contact]
[contact]

[name] (Sub-Investigator)

Pediatrics, Environmental Medicine & Population Health, NYU Grossman School of Medicine
Director and PI of NYU CHES Study
[name]
[contact]
[contact]

[name], MS (Sub-investigator)

Research Scientist, Lab Manager, Department of Pediatrics, Division of Environmental Pediatrics, NYU Grossman School of Medicine
[name]
[contact]
[contact]
(Analyze phthalate and bisphenol levels in urine and breast milk)

[name] (Sub-Investigator)

Research Data Associate, Department of Pediatrics, Division of Environmental Pediatrics, NYU Grossman School of Medicine
[name]
[contact]
[contact]
(Recruitment, consenting, project management, and data collection)

[name] (Study Team Member)

Assistant Professor, Department of Pediatrics, NYU Grossman School of Medicine
[name]
[contact]
[contact]
(Assist in analysis of urine and breast milk)

CONFIDENTIAL

This material is the property of the NYU Langone Health. Do not disclose or use except as authorized in writing by the study sponsor
Behavioral Intervention Template Version: 18 July 2022

1 Introduction, Background Information and Scientific Rationale

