2.2 Secondary Objectives

The secondary and exploratory objective for this study is to compare urinary phthalate and bisphenol exposure levels in the intervention and non-intervention groups, as well as between mothers and children in the control group

3 Study Design and Endpoints

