6.1 Study Procedures/Evaluations

6.1.1 Study Specific Procedures

Biospecimen Collection:

- Biospecimens (1.8mL of maternal breast milk, 1.8mL of maternal urine, and 1.8 mL of infant urine) will be collected at one study visit approximately 2-3 months after enrollment. Biospecimen collection will occur either after a routine well-visit or at the participant's home. If a home visit occurs, study staff will go to the participant's home. Refer to Section 6.2 for more details.

Data Collection:

- Participant's electronic medical record will be used to monitor when they have delivered.
- Either the infant's medical record or the NYU CHES study records will be used to obtain birth weight and length for analysis.
- NYC CHES study questionnaire data that participants previously completed under the NYU CHES study will be pulled from the NYU CHES study database.

CONFIDENTIAL

- We will create a new database for the Diaper Study where we will store all Diaper Study-related results along with demographic and NYU CHES study questionnaire data to be pulled from the NYU CHES database.

Questionnaire Administration:

- Participants will be asked to complete a brief adherence questionnaire at three postpartum time points.
 - Questionnaire will be administered over the phone by study personnel 2 weeks and 6 weeks after diaper intervention has begun.
 - Questionnaire will also be administered during the single study visit.
- It will take less than 5 minutes to complete questionnaire.
- Questionnaire responses will be entered into REDCap by study personnel.
- The purpose of the questionnaire is to assess if the diaper delivery service is working smoothly for the mother and to gauge adherence to group assignment.
- Questionnaire data collected from this study will be shared with qualified researchers on the NYU CHES study.

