6.2.4 Laboratory Evaluations

Chemical analyses. Phthalate metabolites and bisphenols will be analyzed at the NYU Human and Environmental Exposure Assessment Facility Core lab under the supervision of [name].

Bisphenols. Eight bisphenols (BPA, BPAF, BPAP, BPB, BPF, BPP, BPS, and BPZ) will be determined by HPLC-ESI-MS/MS. Concentrations of individual bisphenols will be adjusted for creatinine (Cr) as described below. We will also sum molar concentrations of all individual bisphenols for a total bisphenol concentration.

Phthalate metabolites. Quantitative detection of 22 phthalate metabolites will also involve HPLC-ESI-MS/MS.²² Urine samples will be processed using enzymatic deconjugation of glucuronidated phthalate monoesters, followed by solid phase extraction coupled with reverse-phase HPLC-ESI-MS/MS. Individual phthalate metabolite concentrations will be adjusted for Cr as described below. We will also sum metabolites of parent compounds di-2-ethylhexyl phthalate (DEHP), as well as di-isononyl phthalate (DINP) and di-*n*-octyl phthalate (DNOP), as DINP, DNOP, and di-isodecyl phthalate (DIDP, represented by its metabolite mono-carboxyl isononyl phthalate [mCINP]) are increasingly replacing DEHP in response to consumer advocacy and legislative activity.²³

Creatinine. To account for urinary dilution, urinary Cr will be analyzed using HPLC-ESI-MS/MS as described elsewhere²⁴ and chemical concentrations will be adjusted for Cr via a transformation described by Kuiper et al.,²⁵ with an alternate adjustment method by O'Brien et al.²⁶ and no adjustment explored in sensitivity analyses.

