9.1 Statistical and Analytical Plans

There will not be a formal SAP in this study, as it is a pilot with only 10 participants. Demographics will be compared between members of the intervention and control groups to assess the success of the randomization process. T-tests will be used to compare phthalate metabolite and bisphenol levels between the two groups and correlations of chemical levels will be run comparing mothers and infants in the control group.

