9.2 Statistical Hypotheses

Aim 1: H1: We will successfully recruit participants from within an existing cohort study and collect biosamples from participants and their children in a single follow-up study visit.

Aim 2: Chemical levels will be higher among infants in the control group vs. the intervention group. There will be no difference in average chemical concentrations between the two groups of mothers. Among controls, different chemicals will be present in breast milk vs. infant urine.

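### Correlating control mothers with their infants cannot show relative prevalence, and no Section 9 analysis names the maternal urine that the urinary objective calls for

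*Combined protocol and SAP*

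**What the plan says.** **Planned analysis.** Section 9.4.2 states: "We will also assess correlations of concentrations of individual bisphenols and phthalate metabolites between mothers and children from the control group". The purpose is given as "to assess the relative prevalence of these chemicals in diet (measured in maternal breast milk) vs. baby products (infant urine". Section 9.1 repeats the plan without naming a maternal specimen: "correlations of chemical levels will be run comparing mothers and infants in the control group".

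**Protocol Summary, Statistical Analysis entry.** Here distributions are to be compared, between the two infant groups "and also between mothers and children from the control group to assess the relative prevalence of particular bisphenols or phthalates in diet". Correlation is not mentioned.

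**Hypothesis and objective.** Section 9.2 (and H2 in 1.2) states: "Among controls, different chemicals will be present in breast milk vs. infant urine". Section 2.2 sets the objective as to "compare urinary phthalate and bisphenol exposure levels in the intervention and non-intervention groups, as well as between mothers and children in the control group". Aim 2 in the Protocol Summary and in 1.2 is also worded as urinary.

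**Specimens.** Section 6.1.1 collects "1.8mL of maternal urine" along with milk and infant urine, and Sections 3.1 and 6.3.5 agree. The Endpoint entry of the Protocol Summary says these specimens are for chemical testing, and 3.1 has urine assayed. But 3.2.1 counts two specimens, milk and infant urine; 3.2.2 lists none; and 9.4.2 gives the secondary endpoints as concentrations in milk and infant urine. No analysis in Section 9 names maternal urine.

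**Dilution.** Section 6.2.4: "To account for urinary dilution, urinary Cr will be analyzed". A main adjustment, an alternative adjustment and no adjustment are planned. No adjustment is described for milk.

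**The concern.** The question put to the data is about level and presence: which chemicals predominate in the mother's milk and which in the infant's urine. The statistic chosen is about co-variation: whether mothers with higher values of a chemical have infants with higher values of it. These are different quantities. A high r could be taken to mean that milk and products contribute alike, and a low r that the sources differ; neither follows.

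At stake are the second half of Aim 2 and the third statement of H2. As Section 9 stands, the analysis named for them does not bear on them. The Protocol Summary and Section 9 also leave two different analyses for one purpose, and the maternal specimen for the urinary comparison is unsettled. Both choices could then be made after the results are seen.

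**Working it through.** **1. Number of pairs.** Section 9.4.5 gives 10 participants, 5 per group, set by budget. 10/2 = 5 control pairs. There is no power calculation to reproduce.

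**2. Effect of a difference in level on a correlation.** Let M be the maternal and I the infant values of one chemical, and multiply all infant values by k > 0:

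r(M, kI) = k·cov(M, I) / [SD(M)·k·SD(I)] = r(M, I).

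On the log scale, ln(kI) = ln k + ln I only adds a constant. Ranks do not change either. So Pearson, log-Pearson and Spearman coefficients are all unaffected.

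Illustration with made-up values, M = 1.0, 1.6, 2.2, 3.1, 4.0 and I = 1.3, 1.2, 2.9, 2.6, 4.4:

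| k | Pearson | Spearman | log-Pearson | Infant/mother geometric mean ratio |
|---|---|---|---|---|
| 0.1 | 0.917 | 0.800 | 0.892 | 0.10 |
| 1 | 0.917 | 0.800 | 0.892 | 1.03 |
| 10 | 0.917 | 0.800 | 0.892 | 10.3 |
| 100 | 0.917 | 0.800 | 0.892 | 103 |

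Relative level changes a thousandfold and no correlation moves. This does not depend on n.

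**3. Presence.** The third H2 statement expects some chemicals in one specimen and not in the other. If a chemical were found in no milk sample and the undetected values were set to one constant, SD(M) = 0 and r would be undefined. The case of most interest to the hypothesis is the one a correlation cannot handle. Section 11 gives limits of detection, but no rule for values below them is stated.

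**4. Sections side by side.** Protocol Summary: compare distributions. Sections 9.1 and 9.4.2: correlate. Section 2.2: urinary comparison of mothers and children. Section 9.4.2: milk for the mother, urine for the infant. Milk and creatinine-adjusted urine are not on a common scale. Breastfeeding, or the intention to breastfeed, is an inclusion criterion (4.1), so infant urine reflects milk as well as products.

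**5. What a within-pair ratio would give.** For 5 pairs, the 95% CI of the geometric mean ratio is the estimate ×/÷ exp(t·SD/√5), with t = 2.776 on 4 df. The SD of the log ratio is not in the documents, so a range is assumed:

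| Assumed SD | CI factor |
|---|---|
| 0.5 | 1.86 |
| 0.8 | 2.70 |
| 1.0 | 3.46 |
| 1.5 | 6.44 |

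This is imprecise, but it estimates the quantity that the objective names.

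**6. Precision of the correlation, for context only.** Assuming two-sided 0.05 (no alpha is stated), the critical |r| at n = 5 is t/√(df + t²) = 3.182/√(3 + 10.13) = 0.878. For r = 0.5, Fisher z gives 0.549 ± 1.96/√2, a 95% CI of −0.68 to 0.96. With 8 + 22 = 30 chemicals, each tested at 0.05 and all nulls true, 30 × 0.05 = 1.5 would be significant by chance.

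**The case against.** The strongest defence is that Aim 2 is exploratory in a pilot sized by budget. Section 9.4.5 concedes that there is neither the power nor the room for multiplicity control. The Protocol Summary already plans a comparison of distributions for this purpose, and every specimen's concentrations will exist, so presence can be tabulated. Milk is the plan's deliberate measure of diet and a route of exposure for breastfed infants. Section 6.2.4 already includes an unadjusted analysis.

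Much of this stands, and it rules out several stronger readings that a reader might infer:

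- *That maternal urine is never used.* It is collected for chemical testing and urine is assayed. Section 9.1 names no maternal specimen, so it does not exclude urine. What holds is that 3.2 and 9 do not name it.
- *That H2 can be neither supported nor refuted from this study.* The data to tabulate presence will exist, and the Protocol Summary points to a usable comparison. The defect lies in the analysis that Section 9 names.
- *That small n and multiplicity are the fault.* The figures in step 6 are correct arithmetic, but they concern limits that the protocol admits, and they assume an alpha and tests that 9.4.2 does not specify.
- *That using controls only is an error.* The question is diet against conventional products. Intervention infants receive products free of these chemicals, so pooling would change the question.
- *That milk is the wrong specimen.* It suits the diet question in 9.4.2. It does not deliver the urinary comparison in 2.2.

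The defence does not reach the main point. Being a pilot excuses imprecision, not a statistic that targets another quantity.

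**Conclusion.** The point holds. As Sections 9.1 and 9.4.2 are written, the mother-infant correlation cannot address relative prevalence or the presence hypothesis at any sample size. It also disagrees with the Protocol Summary. The role of maternal urine in the urinary objective is left unstated in the endpoint and analysis sections.

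The consequence is confined to the mother-child part of an exploratory aim; the primary feasibility aim is untouched. The plan should be changed because the correction is cheap, but this is not a fatal flaw.

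The invariance result is algebraic and needs no assumed figures. It does rest on reading 9.4.2 as one correlation per chemical across pairs, which its reference to individual chemicals indicates. The interval widths in step 5 rest on assumed SDs.

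**What to change.** In 9.1 and 9.4.2, replace the correlation as the main mother-infant analysis with the following, in the control pairs:

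- **Detection frequency** of each chemical in milk, infant urine and maternal urine, tabulated within pair. This addresses the third H2 statement.
- **Within-pair infant/maternal urine geometric mean ratio** for each chemical with a 95% CI, creatinine-adjusted and unadjusted (6.2.4 already plans both). This addresses the urinary comparison in 2.2. State a rule for values below the limit of detection.
- **Milk concentrations and profiles**, reported descriptively as the dietary measure. Note that milk and creatinine-adjusted urine are not on a common scale, and that breastfed infants' urine reflects milk as well as products.

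Any correlations kept should be descriptive, with CIs, and not interpreted as relative prevalence. Showing the intervention pairs separately is optional.

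Align the Protocol Summary, 2.2, 9.1 and 9.4.2. List maternal urine among the secondary endpoints, and say which maternal specimen serves the hypothesis of no difference between the two groups of mothers.

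Cost: wording only. The specimens and assays are already planned. The drawback is that ratios from 5 pairs are imprecise and can only be descriptive.

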1.2 Rationale

Infants are highly exposed to phthalates and bisphenols, ubiquitous EDCs that have both estrogenic and anti-androgenic activity. Phthalates and bisphenols have been detected in a range of infant care products, including diapers,^{17,18} wipes, baby lotions, soaps, shampoos,¹⁹ and plastic baby bottles.²⁰ Exposure is magnified by infants' high surface-to-volume ratio and by the increased efficiency of dermal absorption via the thin skin surrounding their enlarged genitalia.²¹ This pilot study will test whether intervening on these sources of exposure during the critical period of minipuberty affects infants' body burden of phthalates and bisphenols. If successful, this protocol may be scaled up and eventually evidence may be used to inform regulation of chemicals contained in infant care products and educational outreach programs to protect children's health.

Aim 1: To assess the feasibility of an intervention designed to reduce infant phthalate and bisphenol exposure.

H1: We will successfully recruit participants from within an existing cohort study and collect biosamples from participants and their children in a single follow-up study visit.

Aim 2 (exploratory): To compare urinary phthalate metabolites and bisphenols between the intervention and non-intervention groups, as well as between mothers and children in the control group.

H2: Chemical levels will be higher among infants in the control group vs. the intervention group. There will be no difference in average chemical concentrations between the two groups of mothers. Among controls, different chemicals will be present in breast milk vs. infant urine.

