3.2 Study Endpoints

3.2.1 Primary Study Endpoints

The primary endpoint, needed to fulfill Aim 1, is when the total number of participants (N=10) have used their assigned baby products for three months and the two biospecimens (maternal breast milk and infant urine) have been collected from all participants.

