5.1 Study Intervention Description

The study intervention is supply of baby products. The intervention group (n=5) in this study will be assigned use of phthalate- and bisphenol-free baby products and subscription to a cloth diaper service. Participants assigned to the control group (n=5) will receive disposable diaper delivery and conventional baby products.

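### Diet-versus-baby-products attribution rests on control pairs alone, which cannot separate the assigned products from other infant-only sources; the planned between-arm contrast is not tied to the question

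*Combined protocol and SAP*

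**What the plan says.** Section 9.4.2 has two analyses of the concentrations. The first is a t-test between the two infant groups, described as an assessment of the intervention's effectiveness. The second is a set of correlations "between mothers and children from the control group to assess the relative prevalence of these chemicals in diet" (taken from milk) relative to baby products (taken from infant urine).

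The restriction to controls recurs. Section 9.1 says "correlations of chemical levels will be run comparing mothers and infants in the control group". The Statistical Analysis row of the Protocol Summary compares chemicals "also between mothers and children from the control group to assess the relative prevalence of particular bisphenols or phthalates in diet" and labels the other side "baby products (reflected in infant urinary concentrations"). The last clause of H2, in sections 1.2 and 9.2, reads "Among controls, different chemicals will be present in breast milk vs. infant urine".

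The intervention pairs are sampled too: the primary endpoint in section 3.2.1 is reached when "the two biospecimens (maternal breast milk and infant urine) have been collected from all participants", and sections 3.1 and 6.3.5 add maternal urine. No section plans a mother-infant comparison in the intervention arm.

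**The concern.** The labels assume that whatever is in a control infant's urine and not explained by milk came from the assigned products. Section 5.1 gives these infants the product source ("Participants assigned to the control group (n=5) will receive disposable diaper delivery and conventional baby products"), and breastfeeding is an entry criterion, so they have the milk source as well. They also have every other exposure, and control pairs contain no infant from whom the conventional products have been withheld.

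At stake is a false attribution. A chemical found in control infants' urine and not in their mothers' milk could be reported as product exposure even if intervention infants carry it at the same level. Sections 1.1 and 1.2 say the study will gauge exposure through infant care products and may eventually feed into regulation, so this reading is likely to be quoted beyond the pilot. Recruiting more control pairs would not cure it.

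**Working it through.** The plan has no figure to reproduce. Section 9.4.5 sets 10 participants (5 per group) by budget, and no alpha, effect size, SD or source share is given. The check is whether control-pair data can in principle tell product exposure from other exposure.

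**Inputs from the documents**
- Control infants have milk (section 4.1, criterion 5; exclusive breastfeeding is not required) and conventional products (section 5.1).
- Other sources: section 1.2 calls the chemicals ubiquitous and lists plastic bottles. The supplies described in the Summary and section 5.1 do not mention bottles, although the Summary's lists are only examples. Section 6.2.1 collects infant urine in an adhesive bag and milk in a cup. Section 6.2.2 has the devices tested, so the protocol accepts that they might contribute.
- Intervention infants are designed to lack the conventional products (section 5.1).

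**Model (assumed, not in the documents).** Control infant urine = D (via milk) + P (assigned products) + O (infant-only other source). Intervention infant urine = D + O. Milk tracks D. Components are independent with coefficient of variation (CV) 0.6, so each variance is (0.6 × mean)². Then:
- control-pair correlation r = √[Var D / (Var D + Var P + Var O)]
- non-milk share = (P + O)/(D + P + O)
- true product share = P/(D + P + O)
- control minus intervention infant mean = P

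| D, P, O | r, control pairs | Non-milk share | True product share | Difference between arms |
|---|---|---|---|---|
| 1, 1, 0 | √(0.36/0.72) = 0.71 | 1/2 = 50% | 1/2 = 50% | 1.0 |
| 1, 0, 1 | √(0.36/0.72) = 0.71 | 1/2 = 50% | 0/2 = 0% | 0.0 |
| 1, 0.5, 0.5 | √(0.36/0.54) = 0.82 | 1/2 = 50% | 0.5/2 = 25% | 0.5 |

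A simulation of 200,000 pairs per row gave the same values. The first two rows agree in everything control pairs can show and differ only in the contrast between arms. That does not depend on the CV: in control infants P and O enter the sum in the same way, so swapping them changes nothing observable.

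**A source shared with the mother behaves differently.** Add a source of mean 1 that enters both milk and infant urine to the first row. The correlation becomes √(0.72/1.08) = 0.82, up from 0.71, so this source would be read as diet.

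**What 5 per arm can recover**
- Estimate the product share as (control mean − intervention mean)/control mean. For the third row (true value 25%), 95% of simulated results fall between about −5% and 47% at CV 0.4, −24% and 55% at CV 0.6, and −67% and 67% at CV 1.0.
- A 5 versus 5 t-test (two-sided 0.05 assumed) has 80% power only at a standardised difference of about 2.0, and 29% at 1.0.
- The control-only correlation is also imprecise. An observed r of 0.5 in 5 pairs has a 95% interval of tanh(0.549 ± 1.96/√2) = −0.68 to 0.96, and |r| must exceed 0.878 for p < 0.05.

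**The case against.** The strongest reply is that the needed contrast is already planned. The t-test between infant groups removes sources common to both arms, and it would show a chemical present equally in control and intervention infants. H2 puts that contrast first and also expects the two groups of mothers not to differ. This stands: a reader might infer that the trial plans no comparison able to isolate the products, and that would be wrong. What remains is that section 9.4.2 gives the t-test to effectiveness and source attribution to a separate control-only analysis, with nothing requiring the two to be read together.

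Two further stronger readings are tempting and also fail.
- A reader might infer that every third source is credited to products, whatever statistic is used. The planned statistic is a correlation, and a shared source that enters milk would raise it and be read as diet. The clear case is an infant-only source.
- A reader might infer a bias of known size. No planned statistic produces a source share, and milk and creatinine-adjusted urine (section 6.2.4) are not on one additive scale. The percentages above show that the sources cannot be separated; they do not estimate the error.

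The intervention pairs are also an imperfect reference. The study is open-label with alternating assignment (section 9.4.6), and adherence is self-reported (sections 9.3 and 9.4.4). Finally, Aim 2 is exploratory and section 9.4.5 declares the study underpowered. That limits the consequence to interpretation, but it does not make the attribution rule sound, because imprecision and misattribution are different faults.

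**Conclusion.** The concern holds in limited form. Control pairs alone cannot distinguish exposure from the assigned products from exposure through another infant-only source, and the plan's labels would call both baby products. Taken literally, the label on infant urine also counts what arrives through milk.

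The size of the error cannot be computed from the documents. The 50% versus 0% example rests on an assumed additive model, but the failure to separate the two sources does not depend on the chosen values.

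Here baby products means the assigned supply. Section 1.2 lists bottles among infant care products, so a bottle counts as another source only in the sense that the described supply does not mention it. The collection bag is the cleaner example, and section 6.2.2 gives some protection by testing the devices.

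The contrast between arms resolves the question only if participants adhere and other exposures are similar in both arms. With 5 per arm it does so descriptively. No confirmatory result is affected.

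**What to change.** Change sections 9.1 and 9.4.2, the Protocol Summary and the last clause of H2 (sections 1.2 and 9.2) as follows.

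1. For each chemical, report detection and concentrations in milk, maternal urine and infant urine for both arms, and run the same mother-infant comparison in the intervention pairs.
2. Attribute a chemical to baby products only when infant urinary levels or detection are higher in control than in intervention infants. Use the between-arm infant difference on the log scale, with its 95% interval, as the main evidence.
3. Give an infant-to-mother ratio only as a supplement, name the maternal matrix, and compute it only where both values exceed the limit of detection. It cannot be computed in the case of most concern, a chemical absent from milk.
4. State that the attribution is descriptive with 5 per arm and assumes adherence and similar other exposures in both arms.

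**Cost.** Wording and a few extra tables, with no new participants, samples or assays. The downside is a more cautious claim with wider intervals. The interval for the difference between arms is a factor of exp(t(0.975, 8) × SD × √(2/5)) either way: 2.07, 3.21 and 4.30 for assumed log SDs of 0.5, 0.8 and 1.0. At 0.8, a one-arm mean of 5 has a factor of exp(t(0.975, 4) × 0.8/√5) = 2.70. The plan proposes no such one-arm interval, so 2.70 is only a benchmark.
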